14.8.3. YSI Retention

All YSI values will be captured and retained in OC-RDC database. However, if the difference between Result A (black) and Result B (white) is greater than (>) 5%, the YSI values will not be included in the analysis dataset.

14.9. Statistical Model and Analyses of Primary Endpoint

Sensor values from primary sensor will be compared to YSI plasma glucose values during YSI FSTs. A within 20% mean agreement rate (± 20 mg/dL (1.1 mmol/L) when Reference BG less than or equal to (\leq) 80 mg/dL (4.4 mmol/L) between Enlite Sensor values and YSI plasma glucose values during YSI FST days defined as μ will be evaluated against the null Hypothesis:

$$H_0: \mu \leq 60\%$$

$$H_1: \mu > 60\%$$

- Statistical testing

One sample T test will be used for the analysis of the primary endpoint. The 97.5% lower confidence limit of the mean agreement rate will be tested against corresponding threshold.

- Missing data
No imputation for missing data will be performed.
- Pass/Fail Criteria
The study pass/fail criteria is based on statistical hypothesis of the primary endpoint. If the 97.5% lower confidence limit is greater than 60%, the study will be considered as success.
- Justification for Exclusion of Particular Information from the testing of the Hypothesis
Not Applicable

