9.4. Randomization and Treatment Assignment

Investigational Centers will receive this randomization assignment generated electronically in the study database from Medtronic. The first randomization scheme assigns the subjects to one of the following sensor wear days (Day 1, 3-4, or 6) which determines when they will be participating in the in-clinic YSI FST.

Once subject is assigned to the study group, subjects will stay in that randomization group during the study.

In addition, at the end of the study (Visit 5), another randomization scheme will be done to assign the primary and secondary sensor for each subject.

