14.5. Sample Size and Power

The sample size selected is based on the primary analysis of the primary effectiveness endpoint (i.e., accuracy), agreement in comparative readings of paired sensor and YSI glucose readings.

Based on previous study, using one sample T test (formula provided below) with a level of 0.975 (one sided), β of 0.8, μ_0 is 0.6, μ_α is 0.72 and σ is 0.32:

$$n = \sigma^2 \frac{(t_\alpha + t_\beta)^2}{(\mu_0 - \mu_\alpha)^2}$$

It is indicated that a sample size of 58 will have power greater than or equal to 80% to demonstrate that the overall agreement rate is greater than 0.6. Considering 20% drop out, we need to enroll 72 subjects.

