6.9 Significance Level and Statistical Analysis Software

For the statistical analysis of the primary endpoint and secondary endpoints, the level of significance will be set at one-sided 0.025. The level of significance of tests performed on other indicators will be set at two-sided 0.05 level (except special cases). SAS® 9.4 statistical software and R3.5.2 are applied for statistical analysis.

7. Indicators and Statistical Analysis Methods

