7.6 Primary Endpoint

For the primary endpoint 20/20% consistency rate analysis, both the analyses based on measurement level and subject level will be provided. One sample T test will be used for the analysis of the primary endpoint based on subject level. Both the approximate normal distribution method and Clopper-Pearson method will be used to estimate primary endpoint based on measurement level. The 95% confidence limit of mean agreement rate will be calculated and tested against corresponding threshold pre-specified in protocol.

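### The primary t-test ignores the randomised FST day and fixes no day weights; if agreement differs by wear day this costs a little precision, and with uneven losses it also shifts the mean and the type I error

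*Protocol*

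**What the plan says.** Protocol 9.4 states: "The first randomization scheme assigns the subjects to one of the following sensor wear days (Day 1, 3-4, or 6"). Each subject undergoes one FST (protocol 6), so a subject's agreement rate reflects one wear window: 1–25, 49–97 or 121–145 hours (protocol 9.2.3.1, Table 2). No allocation ratio is given.

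For the primary endpoint, protocol 14.9 says "One sample T test will be used for the analysis of the primary endpoint" and SAP 7.6 says "One sample T test will be used for the analysis of the primary endpoint based on subject level". Neither mentions FST day. The success rule in protocol 14.9 is: "If the 97.5% lower confidence limit is greater than 60%, the study will be considered as success". FST day enters only as descriptive subgroups and by-day summaries (protocol 14.12.5; SAP 7.9 and 7.9.5).

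Protocol 14.5 sizes the trial on one overall SD: the alternative mean "is 0.72 and σ is 0.32", "with a level of 0.975 (one sided"), concluding that "a sample size of 58 will have power greater than or equal to 80" per cent. SAP 6.9 confirms the test level: "the level of significance will be set at one-sided 0.025". Missing data are not imputed, and a subject needs at least one sensor–YSI pair to enter the efficacy set (protocol 14.6; SAP 6.3 and 6.5).

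**The concern.** The trial randomises by wear day and then analyses as if it had not. Two consequences are possible.

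- **Precision.** If true agreement differs between wear days, a plain one-sample SD includes that difference. The SE is then larger, and the lower limit compared with 60% lower, than the stratified design requires.
- **Meaning of mu.** The objective is accuracy over six days, but nothing fixes how the three windows combine. The plain mean weights each day by its evaluable count. If losses differ by day, the estimate moves away from the planned mix, and the pass/fail decision moves with it.

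Uneven loss is plausible. A later FST means longer exposure to dislodgement beforehand, and re-insertion is allowed only once (protocol 9.6). Subjects without a pair leave the analysis.

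**Working it through.** **Inputs from the documents.** Null 0.60, alternative 0.72 (difference 0.12), SD 0.32, one-sided alpha 0.025, n = 58. The printed level of 0.975 and beta of 0.8 are read as the confidence level and the power.

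**Assumptions (not in the documents).** The spread of agreement between days, the evaluable counts by day, a 1:1:1 allocation, and normal data in the simulations.

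**1. The plan's own figure.** n = 0.32² × (t₀.₉₇₅ + t₀.₈)² / 0.12². With 57 df this is 0.1024 × (2.003 + 0.848)² / 0.0144 ≈ 57.8, so 58. Noncentral-t power is 0.795 at n = 57 and 0.802 at n = 58. The stated 58 reproduces.

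**2. Precision, equal groups.** For three equally spaced day means with lowest-to-highest spread s, the between-day variance is s²/6. The within-day SD is √(0.32² − s²/6), the SE is that divided by √58, and there are 55 df. The plain SE is 0.32/√58 = 0.0420.

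| Spread | Between-day share of variance | Within-day SD | SE | SE cut | Power (plain 80.2%) |
|---|---|---|---|---|---|
| 0 | 0% | 0.3200 | 0.0420 | 0% | 80.1% |
| 9 points | 0.00135/0.1024 = 1.3% | 0.3179 | 0.0417 | 0.7% | 80.6% |
| 15 points | 0.00375/0.1024 = 3.7% | 0.3141 | 0.0412 | 1.8% | 81.6% |
| 20 points | 0.00667/0.1024 = 6.5% | 0.3094 | 0.0406 | 3.3% | 82.7% |

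**3. Drift, uneven groups.** Take 22/20/16 evaluable on Day 1, Day 3-4 and Day 6.

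- Day means 78/76/62%: (22×78 + 20×76 + 16×62)/58 = 4228/58 = 72.9%.
- Day means 62/76/78%: (22×62 + 20×76 + 16×78)/58 = 4132/58 = 71.2%.
- Equal weights in either case: 216/3 = 72.0%.

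**4. Type I error.** Keep the first pattern's deviations (+6, +4, −10 points) but set the equally weighted mean at exactly 60%. The between-day variance is (0.06² + 0.04² + 0.10²)/3 = 0.00507, so the within-day SD is √(0.1024 − 0.00507) = 0.312. By simulation at 22/20/16, the plain t-test rejects about 0.037 of the time (separate runs gave 0.036 to 0.038). The stratified mean holds 0.025.

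A more uneven split of 14/20/24, with the lowest-agreement day smallest and equally spaced means, gives about 0.039 at a 10-point spread and 0.053 at 20. With the highest-agreement day smallest (24/20/14), the plain test's type I error falls to about 0.015 or 0.007. Its power at an equally weighted mean of 72% falls to about 0.74 or 0.68.

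**5. Cost of the remedy.** With equal weights, SE = (within-day SD/3) × √(1/n₁ + 1/n₂ + 1/n₃). With no day difference:

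- 22/20/16: 0.32/3 × √0.1580 = 0.0424, power 79.4%.
- 24/20/14: 0.32/3 × √0.1631 = 0.0431, power 78.1%.

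**The case against.** Both effects are conditional. A reader might infer that the error bar certainly carries avoidable variance, or that the estimate is certainly biased. The documents support neither: they give no agreement rate by day, no between-day variance and no losses by day. With no day difference there is nothing to gain and no drift, and stratifying costs a trace of power (80.16% to 80.12% with equal groups). This stands.

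The two halves also pull against each other. The precision gains assume equal groups; the drift assumes uneven ones. At 22/20/16 with a 9-point spread, the equally weighted SE is 0.0421 and power 79.9%, slightly worse than the plain test; at 15 points power is 80.9%. This stands too, so the case for the change rests mainly on fixing what mu means.

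A reader might also infer that Day 6 will be depleted by dislodgement. Protocol 9.6 works against that: dislodgement before the FST, or within its first 5 hours, leads to re-insertion of both sensors and a rescheduled FST in the same randomised group, and one pair keeps a subject in the analysis. Loss is limited but not excluded, because re-insertion happens once.

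Nor is the plain test generally liberal. With near-equal groups it is slightly conservative when days differ (type I error about 0.023 at 10 points, 0.019 at 20). The planned by-day summaries would reveal day differences but would not correct the primary estimate.

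Finally, one-third weights are a choice. The windows last 24, 48 and 24 hours, so time-based weights would be 1:2:1. That is a reason to state the weights, not to leave them to the evaluable counts.

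**Conclusion.** The point holds in conditional form. Both documents omit the randomised FST day from the primary test, and neither fixes day weights for mu. If agreement differs by day, the precision loss is small: 0.4 to 2.5 power points over assumed spreads of 9 to 20 points with equal groups. If evaluable numbers also become uneven, the plain mean drifts by about 1 point at 22/20/16, against a planned 12-point margin. Type I error for the equally weighted mean can then rise from 0.025 to about 0.037, or fall below 0.025 if the losses run the other way. The drift matters more, because it affects what the pass/fail decision refers to. All these sizes rest on assumed spreads and counts. It would be wrong to conclude that the sample size of 58 is in error: it reproduces, and it matches the unstratified test it was computed for.

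**What to change.** In protocol 14.9 and SAP 7.6:

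- State the allocation ratio and fix the day weights in advance at that allocation (one third each if 1:1:1).
- Estimate mu as the weighted mean of the three FST-day means of subject-level agreement, with the SE from the pooled within-day variance on n − 3 df.
- Compare the one-sided 97.5% lower limit with 60%, as now.
- Report evaluable subjects by FST day, and keep the unstratified t-test as a sensitivity analysis.

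The cost is a short text change in each document, two degrees of freedom, and slightly lower precision if the groups end uneven: with no day difference, power of about 79.4% at 22/20/16 or 78.1% at 24/20/14, against 80.2%. The threshold, sample size and data collection are unchanged.

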14.10. Analyses of Secondary Endpoints

Sensor values from primary sensor will be compared to YSI plasma glucose values during YSI FSTs. And the 95% Confidence Interval of MARD, mean rate in Zone A+B of Clarke Error Grid and Consensus Error Grid will be provided.

14.11. Numbers of Reading in the Low and High Ranges

Every effort to safely collect data in the low and high range via the hyperglycemic and hypoglycemic challenge will be made

14.12. Other Descriptive Endpoints

Other descriptive endpoint analysis will be repeated for each dataset under 14.8

14.12.1. Difference Tables Comparing Sensor and Reference Readings

Number and percentage of paired data points within 10%, 15%, 20%, 30%, 40%, 50%, 60%, 70%, 80%, 90% and 100% of the reference method (YSI for in-clinic portion and meter BG for home-use portion) will be summarized.

Number and percentage of paired data within 10 mg/dL, 15 mg/dL, 20 mg/dL, 30 mg/dL, 40 mg/dL, 50 mg/dL, 60 mg/dL, 70 mg/dL, 80 mg/dL, 90 mg/dL and 100 mg/dL Of the reference method (YSI for in-clinic portion and meter BG for home-use portion) will be summarized.

14.12.2. Sensor Calibration

Characteristics of Enlite Sensor calibration will be evaluated by:

- Rate of change (less than (<)-4.0 mg/dL/min, -4.0 to -2.5 mg/dL/min, -2.5 to -2.0 mg/dL/min, -2.0 to -1.5 mg/dL/min, -1.5 to -1.0 mg/dL/min, -1.0 to +1.0 mg/dL/min, +1 to +1.5 mg/dL/min, +1.5 to +2.0 mg/dL/min, +2.0 to +2.5 mg/dL/min, +2.5 to +4.0 mg/dL/min, and greater than (>) +4.0 mg/dL/min).
- Rate of change arrows that are displayed to users
- First calibration SMBG value ranges (40 - 70 mg/dL, 70 - 180mg/dL and 180 - 400 mg/dL): the numerical Sensor Glucose Value (SGV) accuracy will be evaluated against YSI stratified by the first calibration SMBG value up to the second calibration SMBG.

14.12.3. Clarke Error Grid Analysis (EGA) of Paired Sensor and YSI and Reference Values

1) Description

Clarke EGA separates paired observations into five zones of clinical significance. The presence and severity of possible treatment error based on interstitial glucose assay evaluated by the sensor defines the five zones. Zone A represents the absence of treatment error, where the evaluation method and the reference method are within 20% of one another or in which both methods indicate hypoglycemia. Zone B represents cases where the two methods disagree by more than 20%, but do not lead to treatment error. Zones C, D, and E represent increasingly large and potentially harmful discrepancies between the evaluation and the reference method. If the method under evaluation has a high percentage (greater than (>) 90%) of its pairs in Zones A and B, then it is considered clinically acceptable [Clarke et al, 1987].

2) Statistical analysis

Summary statistics (N, %) for each of the zones, as well as combined Zones A and B, will be calculated.

In order to evaluate differing levels of accuracy at various YSI defined glucose levels, the number and percentage of paired observations falling into Zones A, B, A+B, C, D, and E will be provide form YSI glucose ranges of 40-80 mg/dL, greater than (>) 80-120 mg/dL, greater than (>)120-240 mg/dL, and greater than (>) 240 mg/dL.

All analysis performed using the Clarke Error Grid comparing the paired sensor and YSI reference glucose values will be duplicated using the Continuous Error Grid [Clarke et al, 1987] and the Consensus Error Grid [Parkes et al, 2000].

14.12.4. Precision Analysis

Precision analysis will be performed for the two sensors worn by the same subject in the same location. The recorder connected to the Enlite sensor will be re-analyzed using the exact calibration SMBG used in iPro2 Device.

14.12.5. Other Accuracy Analyses

The ARE, the absolute differences between the sensor and YSI relative to the YSI reference will be calculated for each day separately. Summary statistics will include its mean, standard deviation, min, median, and max.

The mean numerical bias, which is the difference between the sensor and YSI values, will be calculated for each day. Summary statistics will include its mean, standard deviation, min, median, and max.

Bland-Altman plots, with 95% CI, will be provided for each of the 3 study days. The paired differences between the sensor and YSI rating will be plotted against the X-axis reference of mean YSI and sensor values.

Descriptive subgroup analysis of Enlite Sensor performance (20% mean agreement rate (± 20 mg/dL (1.1 mmol/L) when Reference BG less than or equal to (\leq) 80 mg/dL (4.4 mmol/L))) will be performed in the following cohorts:

- **FST:**
 - Day 1
 - Day 3-4
 - Day 6

All analysis follow the definitions provided in: Performance Metrics for Continuous Interstitial Glucose Monitoring: Approved Guideline, CLSI POCT05-A [Klonoff et al. 2008].

14.12.6. Home-Use Portion Data Analysis

Data from the home-use portion will be described. Analysis will include but not be limited to: 20% mean agreement rate (± 20 mg/dL (1.1 mmol/L) when Reference BG less than or equal to (\leq) 80 mg/dL (4.4 mmol/L)) for all fingersticks (capillary SMBG) collected, Clarke Error Grid, other accuracy analysis, ARE, bias, correlation between Enlite Sensor and SMBG and Bland-Altman plots. In addition, 20% mean agreement rate (± 20 mg/dL (1.1 mmol/L) when Reference BG less than or equal to (\leq) 80 mg/dL (4.4 mmol/L)) will be described by subgroups of YSI FST. The number of actual calibrations performed per day by study subjects will be tabulated and presented:

- **FST:**
 - Day 1
 - Day 3-4

- Day 6

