7.2.4. CareLink™ iPro Therapy Management Software for Diabetes (MMT-7340) - Desktop Software

CareLink iPro Therapy Management Software for Diabetes(MMT-7340), referred to as CareLink iPro in the CIP, is a PC-based software desktop application. Refer to 10572826DOC for the software version. It will manage the data flow to and from the iPro2; merge sensor and BG meter data to produce glucose sensor values; produce user-friendly graphics and text displaying the data downloaded from the iPro2; store the data on computer and allow for data retrieval in both graphical and textual format.

This software receives the uploaded data via the hardware physical port (USB) of the recorder dock processes and analyzes the uploaded data, and finally generates reports.

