9.2.4.3. Overview training and instructions

Investigational center staff will:

- Train each subject on study procedures (e.g. how to use of Patient Log Sheet)
- Train subjects on use of Study Meter
 - Subject will be instructed to wash his/her hands thoroughly with warm, soapy water, rinse and dry before testing BG
 - Consider best practice to use "second drop" technique, express first drop and wipe away, express second drop for meter BG testing
 - Subjects will be instructed to use only the Study Meter during the course of the study to perform Enlite Sensor calibration of study devices
 - Subjects will also be instructed to record their BG meter data on the Patient Log Sheet
- Train subject on iPro2 wear:
 - Instruct that each iPro2 will be worn with an Enlite Sensor approximately 6 days
 - Instruct subjects that Enlite Sensor(s) will be replaced if it has dislodged any time prior to completing their YSI FST visit (see Section 9.6).
 - Instruct subjects that he/she may be asked to repeat the YSI FST (see Section 9.7)
- Instruct subjects to perform fingersticks (capillary SMBGs)
- Instruct subjects on returning to clinic for early dislodgement of Enlite Sensors.
- Instruct subjects to contact investigational center staff for technical issues and support
- Remind subjects to bring in the Study Meter (for accuracy testing) to FST visit

In addition:

- Assess subjects for the occurrence of any AEs or device deficiencies (see Section 11 and Section 13) at each visit and document on the appropriate source; record event(s) on the appropriate eCRF

Subjects will continue on their current diabetes regimen independent of the study devices.

Subjects will be instructed by the investigational center that they are not to use the study devices (except for the study meter) for the management of their diabetes. The Study Meter may be used for treatment decisions and fingersticks.

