Prior to use, all devices will be prepared by investigational center staff following the instructions in the users' guides. Before distributing to subjects, the clocks in the Study Meter need to be synchronized with a designated study clock at the investigational center. Subjects will be instructed not to change the clocks in these devices. Subjects will be provided a Study Meter to be used to perform fingerstick (capillary SMBG). The investigational center staff will also have to register the subject into CareLink iPro and download the subject's Study Meter later (see Investigator Site Binder for details).

In the event the subject no longer wants to participate in the study after the study procedure training or any time throughout the course of the study including the day of YSI FST, the subject will be withdrawn. This will be documented in the subject study file including the reason for withdrawal and the Exit eCRF will be completed.

iPro2 Setup & Fingerstick Instructions

The investigational center staff will need to perform a charge with the iPro2 prior to subject's visit:

- Refer to iPro2 setup per user guide
- Refer to Table 2 for instructions at YSI FST
- Subjects will be recommended to record the fingerstick value as a calibration within 5 minutes of measuring their BG on the Patient Log Sheet

Fingerstick testing at Home and In-Clinic

A minimum of 4 fingerstick glucose readings per day will be requested and recorded on Patient Log Sheet. Consider best practice to use "second drop" technique, express first drop and wipe away, express second drop for meter BG testing.

Enlite Sensor wear duration during the study:

Investigational center staff will remove the subject's Enlite Sensors after 6 days.

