9.2.6. Visit 5: End of Study

- Subjects will return to the clinic to remove their study devices
- Investigational Center staff will review documentation of time they calculated for T=145 hours where the sensor may be removed at that time or after that time to ensure that the devices are not removed pre-maturely
- Investigational center staff will address questions or concerns from subjects
- Investigational center staff will ask subjects about the occurrence of any AEs or device deficiencies.
- Investigational center staff will:

- Download the iPro2 data from CareLink iPro following completion of the study devices wear
- Obtain subject's Study Meter BG values and enter into CareLink iPro
- Collect subject's Patient Log Sheet
- Provide iPro2 data to sponsor
- Investigational center staff will perform a Skin assessment on the area of each of the Enlite Sensor insertion sites and document in subject source and complete the Skin Assessment eCRFs
- Investigational center staff will collect returned devices (See Table 1 in Device Accountability section) and unused supplies from subjects
- Subjects will complete a questionnaire about their Enlite Sensor experience.
- Primary sensor and secondary sensor will be randomly assigned via RDC.
- An Exit eCRF will be completed at this visit.

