9.10. Glucose and Glycemia Measurements

During the course of the study, the subjects' BG, sensor glucose levels, A1C, and alternate POC BG values will be assessed using the following methods:

- **Daily BG-** Values will be assessed during the study by all subjects using the Study Meter. A QC test will be performed on the meter assigned to each subject before being dispensed and before each YSI FST. The results of the QC test will be documented in the subject's source documents. The QC test will be done following the manufacturer's user guide. Subjects will be trained on the use of the Study Meter per the manufacturer's user guide.
- **YSI FST BG values** -During the YSI FSTs at the investigational center, blood plasma glucose will be determined using the laboratory BG analyzer (YSI).
- **Sensor glucose values** - Assessed using the following methods:
 - Sensor glucose values collected by subject's iPro2 and calibrated by subject's Study Meter.
- **A1C** - Collected at baseline and will be used as demographic information.
- **Alternate POC BG values-** During the YSI FST at the investigational center, alternate POC BG measurements will be used (Study Meter) and the values recorded on the appropriate eCRF (not used for analysis). A QC test will be performed on the alternate POC BG device before each YSI FST. The results of the QC test will be documented in the subject's source documents. The QC test will be done following the manufacturer's user guide.

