14.8.2. Pairing Scheme

All YSI and fingerstick values collected will be presented. , Most of descriptive analyses will include all YSI values, such as those less than (<) 40 mg/dL, or greater than (>) 400 mg/dL as long as Enlite Sensor values are greater than or equal to (\geq) 40 mg/dL or less than or equal to (\leq) 400 mg/dL (displayed to users as Low or High without numerical numbers). Reference glucose values (YSI values or fingerstick values) will be paired with the closest Enlite Sensor value between [0, 5) minutes. The primary Enlite Sensor will be used as a reference for precision analysis. Clarke EGA will be restricted to YSI values of 40-400 mg/dL. The same pairing scheme will be utilized.

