16.3.3. CareLink iPro

During the course of the study, subject's SG values will be collected and assessed from the iPro2. The iPro2 data needs to be downloaded in CareLink iPro desktop database by the investigator or designated Investigational Center staff. The Study Meter data from the Patient Log Sheet needs to be obtained by the investigator or designated Investigational Center staff and entered into CareLink iPro.

The data in the different databases are linked to each other via the SIDs, which is a 9-digit code (313XXXXXX) to prevent subject identification by the sponsor.

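### Home-use accuracy is scored against all Study Meter fingersticks, including those that calibrated the sensor, so these descriptive results are partly circular

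*Protocol*

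**What the plan says.** **Fingersticks as calibrators**

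- Protocol 7.2.4: CareLink iPro will "merge sensor and BG meter data to produce glucose sensor values".
- Protocol 9.10 describes the sensor data as "Sensor glucose values collected by subject's iPro2 and calibrated by subject's Study Meter".
- Protocol 9.2.4.3: subjects are told to "use only the Study Meter during the course of the study to perform Enlite Sensor calibration of study devices". Under the fingerstick instructions they are advised to "record the fingerstick value as a calibration within 5 minutes of measuring their BG on the Patient Log Sheet".
- Protocol 9.2.6: at Visit 5, staff obtain the subject's "Study Meter BG values and enter into CareLink iPro". Protocol 16.3.3 likewise has the logged meter data "obtained by the investigator or designated Investigational Center staff and entered into CareLink iPro".

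**Fingersticks as reference**

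- Protocol 14.12.6 plans a home-use agreement rate "for all fingersticks (capillary SMBG) collected, Clarke Error Grid, other accuracy analysis, ARE, bias, correlation between Enlite Sensor and SMBG and Bland-Altman plots". SAP 7.9 repeats this and adds the Consensus Error Grid. The synopsis and Protocol 5.2.3 list the same endpoint.
- The difference tables (Protocol 14.12.1, SAP 7.9.1) also take the meter as the home-use reference.
- Protocol 14.8.2: reference values, whether YSI or fingerstick, "will be paired with the closest Enlite Sensor value between [0, 5) minutes". SAP 6.6.2 has the same rule.

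**Limits on the overlap**

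- Protocol 7.2.5 says only that a meter value may be used for calibration.
- Protocol 10.1 says that extra readings taken after acetaminophen are not to be used for calibration.

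**The concern.** An accuracy comparison needs a reference that did not help to produce the value under test. Here a calibrating fingerstick goes into the calculation of the sensor trace and is then compared with the sensor value nearest to it in time. Agreement at that point shows, at least in part, how closely the software fits its own input.

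The affected results are the home-use agreement rate, ARD, bias, correlation, error grids, Bland-Altman plots and difference tables. They are descriptive, but they could be given weight. The study objective is accuracy over six days, and each subject has one YSI session of about 7 hours. For the rest of the wear period the meter comparison is the only reference comparison planned. A reader could take a high home-use rate as independent support for accuracy across that period.

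**Working it through.** The plan states no expected value or precision for home-use accuracy, so there is no figure to reproduce. The check follows the data path and then asks what can be said about size.

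**1. Data path.** The subject measures with the Study Meter and logs the value, with advice to log it as a calibration (Protocol 9.2.4.3). Staff enter the meter values into CareLink iPro after wear (9.2.6, 16.3.3). The software combines them with the sensor signal to produce sensor glucose (7.2.4). The analysis uses these retrospective primary-sensor data (Protocol 14.8.1, SAP 6.6.1) and pairs them with every home fingerstick from the same meter (14.8.2, 14.12.6). The loop is closed for any fingerstick that the software uses.

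**2. Search for a rule that breaks the loop.**

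| Place | Effect on calibration readings |
|---|---|
| Pairing: Protocol 14.8.2, SAP 6.6.2 | None |
| YSI retention: Protocol 14.8.3, SAP 6.6.3 | Concerns YSI duplicates only |
| Sensor data retention: SAP 6.6.4 | Removes sensor data beyond 144 functional hours only |
| Missing data: Protocol 14.6, SAP 6.5 | None |
| Changes to planned analysis: SAP 7.13 | None |
| Calibrations per day: Protocol 14.12.6, SAP 7.9 | A daily count, not a flag on each reading |

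The SAP table shells (SAP 9) were not available.

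**3. Size.** Let s be the share of home pairs whose fingerstick was used to calibrate, C the agreement rate in those pairs and N the rate in the others.

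- Pooled rate: P = s·C + (1 − s)·N
- Excess over the non-calibration rate: P − N = s·(C − N)

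The excess is zero if s = 0 or C = N. If s = 1, then P = C and no non-calibration rate can be observed at all. The documents give none of s, C or N, so no value is computed.

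**4. Scale only.** At least 4 fingersticks a day are requested: 4 × 6 days = 24 per subject, and 24 × 60 completers = 1,440. This is a requested number for completers, not a count of analysable pairs. Each pair needs a sensor value inside the pairing window, data beyond 144 functional hours are dropped, and Study Meter values taken as alternate readings during the YSI session are not analysed (Protocol 9.9.2, 9.10).

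**5. How much wear lacks a YSI comparison.** Per subject, 7 / 144 = 4.9% of the wear period is covered by YSI. The session windows are hours 1–25, 49–97 and 121–145. No session is scheduled in hours 25–49 (24 h) or 97–121 (24 h), which is 48 hours in total, or 48 / 144 = one third of the period.

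**The case against.** The strongest reply is that nothing depends on these results. The home-use data carry no hypothesis, threshold or success rule. The primary and secondary endpoints use YSI, which the protocol treats as the gold standard and which does not calibrate the sensor. All of this stands, and it limits the importance of the point. It does not make the home-use figures independent.

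The plan also states openly that the meter calibrates the sensor and that the meter is the home-use reference. That is true, but the reader of a results table would still see one pooled accuracy figure, and a daily calibration count cannot be used to split it.

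The omission is not fully proven. The table shells were not seen, the home-use list is open-ended, and Protocol 14.12.5 and SAP 7.9.5 defer to an external guideline that cannot be checked here. This is a fair reservation, but the method text says all fingersticks, and any different rule belongs in that text.

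Finally, a split may achieve little. Meter values are entered after wear, so the non-calibration set could be small or empty. Any such readings share the meter's systematic error and are a selected group. This also stands, and it is why the fix has a fallback that changes only the label.

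**Conclusion.** The concern holds. As written, both documents score the home-use sensor values against all fingersticks from the meter that calibrates the sensor, and no visible rule separates the calibrating readings. The results are partly circular, and entirely so if the software uses every logged reading.

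The likely effect is that home-use accuracy looks better than independent accuracy. This assumes that the software pulls the trace towards its calibration readings, so that C exceeds N. The documents do not describe the weighting. The size is s·(C − N) and cannot be computed from what is given.

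The damage is confined to descriptive results. The primary endpoint, the secondary endpoints and the pass/fail criterion are untouched. The change is worth making because it is cheap and prevents a misreading, but the trial's conclusion does not depend on it. Confidence is medium, because the overlap and the software's behaviour are unknown.

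**What to change.** Amend Protocol 14.12.1 and 14.12.6 and SAP 7.9 and 7.9.1, and align the synopsis and Protocol 5.2.3, which carry the same endpoint:

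1. Flag each fingerstick by whether the software used it for calibration. If that cannot be exported, flag whether it was entered in CareLink iPro as a calibration.
2. Report home-use results separately for calibration readings, labelled calibration fit, and for non-calibration readings, labelled agreement with the Study Meter.
3. State that non-calibration readings share the meter's systematic bias and are a selected set. Readings after acetaminophen are one example: Protocol 10.1 warns of falsely high sensor values then. This set may therefore understate accuracy.
4. If few or no non-calibration readings exist, label all home-use results as agreement with the calibrating meter and draw no independent accuracy conclusion from them.

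The cost is one flag and one extra table, with no new data collection, but the sponsor must first confirm that a per-reading flag can be obtained. No such export is documented. Protocol 14.12.4 refers to the specific readings used for calibration, although SAP 7.9.4 omits that sentence. Protocol 14.12.2 planned an analysis between the first and second calibrations, which SAP 7.13 dropped because the registration guideline does not require it. Both protocol sections suggest that individual calibration readings were expected to be identifiable. The home-use figures are likely to become less favourable.
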